3.3 Early Withdrawal of Subjects

3.3.1 Criteria for removal from study

A patient will be removed from the study for any following reasons:

- The patient desires to discontinue participation
- The investigator believes that discontinuation is in the best interest of patient

3.3.2 Follow-up for withdrawn subjects

Patients will be informed that participation in this study is voluntary and that they do not have to participate in this research. If patients choose to participate, they have the right to stop any time. If a patient decides not to take part in the research or decides to stop taking part in the research at later date, there will be no penalty or loss benefits to which he/she is entitled. The PI of this study has the right to remove patients from the study without their permission. If the investigator determines that the subject does not fulfill the criteria to be in the study, or the subject's condition becomes worse, he may remove the subject from the study.

Information obtained prior to withdrawal may continue to be used if is necessary for the soundness of the overall research. Furthermore, records of the care that we provided will be retained as long as the law requires.

As this is a single point of care investigation, the process of withdrawal may occur between the time of consent and the administration of sedative. Withdrawal may occur either with a written or vocalized desire to retract one's consent.

If a subject is removed from the study prior to completion, the reason for doing so and the date the subject is discontinued will be documented.

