7.3 Duration of Participation

For all of the subjects it will take 6 months to complete the study. A follow up colonoscopy will schedule and perform 6 months post-procedure to assess recurrence rate.

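### The removal rule in 3.3.2 lets the investigator drop a patient whose condition worsens, at any time, so the 6-month outcome can be lost in a way that depends on how the patient fares

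*Combined protocol and SAP*

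**What the plan says.** Section 3.3.1 lists two grounds for removal: the patient's own wish, and "The investigator believes that discontinuation is in the best interest of patient". Section 3.3.2 goes further: "The PI of this study has the right to remove patients from the study without their permission". It names two grounds for this, failure to meet the study criteria and worsening ("condition becomes worse, he may remove the subject from the study"). Neither section sets a time limit or an objective criterion.

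On data, 3.3.2 says "Information obtained prior to withdrawal may continue to be used if is necessary for the soundness of the overall research", and it requires the reason for and date of removal to be recorded. Despite its title, it describes no follow-up for patients who leave.

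On timing the text disagrees with itself. Section 3.3.2 tells patients that "they have the right to stop any time", but later says "As this is a single point of care investigation, the process of withdrawal may occur between the time of consent" and, the sentence continues, sedation. Section 7.3 says "For all of the subjects it will take 6 months to complete the study".

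Treatment is a single EMR plus Hybrid APC session (7.2). What remains is a 30-day call (7.2.1) and a 6-month colonoscopy that 7.2.2 describes as standard care. Section 8.3 defines the primary endpoint as the proportion of patients with recurrent or residual neoplasia at 6 months, and declares significance if the upper 95% exact limit is below 15%. It names no analysis population and no rule for a missing 6-month result.

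**The concern.** In a trial of repeated dosing, removing a patient who deteriorates at least ends exposure. Here exposure is over once APC has been applied, so the main research effect of a later removal is that the scar examination never enters the dataset. Because the stated ground is the patient's condition, the loss can be related to outcome.

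The decision lies with the investigator, who performs the procedures (16.3) and reviews adverse events (10.5), in a study with no control arm in which the same loss would occur. Enrolment and the power statement both use 40 patients (8.1, 8.2), so there is no allowance for dropout. At stake is whether the primary rate describes everyone treated or only those the investigator kept in the study.

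**Working it through.** **Inputs.** N = 40, null rate 15%, assumed rate 5%, one-sided test, 60% power (8.2). 95% exact binomial limits, success if the upper limit is below 15% (8.3). No numeric alpha is given. Section 8.3 reads most naturally as two-sided limits, but 8.2 describes a one-sided test, so both are shown.

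**The plan's own figure.** Normal approximation, one-sided alpha 0.05:

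- Null standard error: √(0.15 × 0.85 / 40) = 0.0565. Alternative standard error: √(0.05 × 0.95 / 40) = 0.0345.
- Power = Φ[(0.10 − 1.645 × 0.0565) / 0.0345] = Φ(0.207) = 58.2%, close to the stated 60%.

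The removal rule does not affect this figure.

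**Effect of dropping patients.** The exact upper limit for x recurrences in n patients is the Beta(x + 1, n − x) quantile, at 0.975 for two-sided and 0.95 for one-sided limits. A dropped recurrent patient leaves both numerator and denominator. A dropped non-recurrent patient leaves only the denominator.

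| Result | How it arises | Two-sided 95% upper limit | One-sided 95% upper limit |
|---|---|---|---|
| 2/40 | all kept | 16.9%, fails | 14.9%, succeeds |
| 1/39 | 2/40, one recurrent dropped | 13.5%, succeeds | 11.6%, succeeds |
| 3/40 | all kept | 20.4%, fails | 18.3%, fails |
| 2/39 | 3/40, one recurrent dropped; or 2/40, one non-recurrent dropped | 17.3%, fails | 15.3%, fails |
| 1/38 | 3/40, two recurrent dropped | 13.8%, succeeds | 11.9%, succeeds |

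Two recurrences in 40 is not a remote case. At the planned 5% rate, P(X ≤ 2) − P(X ≤ 1) = 67.7% − 39.9% = 27.8%.

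**How large a bias could be.** The documents give no removal frequency, so the following is an assumption shown over a range. Suppose each patient who would recur is removed with probability q, and no other patient is removed. At a true rate of 15% the expected observed rate is 0.15(1 − q) / (1 − 0.15q). The chance of declaring success comes from exact enumeration.

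| q | Expected observed rate | False success, two-sided limit | False success, one-sided limit |
|---|---|---|---|
| 0 | 15.0% | 1.2% | 4.9% |
| 0.10 | 13.7% | 2.2% | 5.2% |
| 0.25 | 11.7% | 5.1% | 7.2% |
| 0.50 | 8.1% | 17.4% | 19.7% |

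This scenario is built to favour the device, since only recurrent patients are lost. It bounds what the wording would permit over that range and does not predict what will happen.

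**The case against.** A reader might infer that the rule erases outcomes and necessarily pushes both recurrence and complication rates down. The documents do not support that, for four reasons.

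- **Data already collected survive.** Section 3.3.2 allows data obtained before removal to be used and requires the reason and date to be recorded, so selective removals would be visible. This stands, with the reservation that use is permitted rather than required. The 6-month result comes later and is not protected.
- **Safety is largely covered elsewhere.** The event that prompts removal precedes it. Sections 10.2 and 20.1.2 require all adverse events to be documented, and 19.2 follows device-associated events until they resolve or stabilise. This stands. What remains exposed is later events, including those the 30-day call would have found, and any discretionary non-use of earlier data.
- **Direction is not established.** Bleeding or pain after the procedure is not linked to recurrence anywhere in the documents. A recurrence is lost only if the removed patient would have recurred, was removed before the 6-month examination, and leaves the denominator, on which 8.3 is silent. Dropping a non-recurrent patient works against the device: under the one-sided limit it turns 2/40 from success into failure at 2/39. This stands.
- **Withdrawal is said to happen before sedation.** Read literally, post-treatment removal would not arise. This does not dispose of the point. The sentence speaks of patients retracting consent, not of removal by the investigator, and it conflicts with the right to stop at any time in the same section and with 7.3.

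It is also fair that best-interest discretion protects participants and should not be taken away.

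**Conclusion.** The point holds as a gap in the plan: a removal rule with no time limit, based on the patient's condition, applied after a one-session treatment, with no follow-up or analysis rule to make good the loss. It permits outcome-dependent loss of the primary endpoint. It does not show that such loss will occur or which way it would run.

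Its importance comes from the margin. One dropped recurrence turns failure into success under the two-sided limit (2/40 to 1/39). Under the one-sided limit it takes two, from 3/40 to 1/38. A general statement that one removal reverses the conclusion would therefore be too strong: it needs exactly two recurrences, the two-sided reading, and a dropped patient who would have recurred. The effect on safety rates is secondary. The change should be made before data exist, because it is cheap and the decision rule is sensitive.

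**What to change.** 1. Reconcile 3.3.1, 3.3.2 and 7.3 on when withdrawal and removal can occur, including the sentence that places withdrawal before sedation.
2. In 3.3.2, separate stopping participation from removal from the analysis. State that worsening or a complication after Hybrid APC is not a reason to end data collection. Leave the investigator's clinical discretion as it is.
3. In 8.3, define the primary analysis population as all patients who received EMR plus Hybrid APC. Collect their 30-day and standard-of-care 6-month results unless consent for data use is withdrawn, and ask withdrawing patients to permit use of the scar result.
4. In 8.3, add a sensitivity analysis that counts missing 6-month outcomes as recurrence. In the example above, 1/39 with one patient missing returns to 2/40 and an upper limit of 16.9%. Say also how a patient whose scar can no longer be examined is classified.

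The cost is protocol wording and one extra analysis, with no new visit or procedure. The downside is follow-up of a few patients who would otherwise be dropped.

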4.0 Recruitment Methods

4.1 Identification of subjects

We will recruit patients presenting with a known ≥ 20 mm polyp prior colonoscopy and referred for resection of this polyp to Hershey Medical Center.

4.2 Recruitment process

All patients in our institute with a known ≥ 20 mm polyp detected at a prior colonoscopy who are referred for colonoscopy procedure will be identified as potential study participants.

4.3 Recruitment materials

Not applicable

4.4 Eligibility/screening of subjects

All prospective subjects undergoing colonoscopy with a ≥ 20 mm colon non-pedunculated polyp will be seen prior to the procedure to discuss and review the details of the study. Interested individuals will be screened to ensure that they meet inclusion and exclusion criteria.

5.0 Consent Process and Documentation

5.1 Consent Process

5.1.1 Obtaining Informed Consent

5.1.1.1 Timing and Location of Consent

Consent and basic demographics will be garnered by the PI, one of the co-investigators or research associate prior to bringing the patient into the endoscopy suite, discussions about the research and obtaining informed consent will occur in curtained endoscopy pre-procedure room. Patients will be given adequate time to review consent form and consult with family if they wish. Patients are not sedated at the time of consent.

5.1.1.2 Coercion or Undue Influence during Consent

Patients will have time to review the consent form and ask questions. Patients will be informed that Colonoscopy procedure will take place even if the patient chooses not to participate in the study.

5.1.2 Waiver or alteration of the informed consent requirement

Partial Waiver of informed consent is requested pre – recruitment purpose. The chart and Medical record review pre-recruitment poses no more than minimal harm to subject (i.e. loss of confidentiality/privacy). Given the number of subjects and the

possibility that not all subjects that look at their medical record may not eligible for the study
this part of research would not be practical without waiver

5.2 Consent Documentation

5.2.1 Written Documentation of Consent

Consent will be performed by the PI, co-investigators or research associate prior to the procedure. A discussion about the research study will be initiated prior to bringing the patient into the endoscopy suite. Written consent will be obtained by the PI, co-investigators or research associate prior to the procedure and that a copy of the signed consent form will be given to the subject. Patients will be informed that colonoscopy procedure will take place even if they chose to decline participation.

5.2.2 Waiver of Documentation of Consent (Implied consent, Verbal consent, etc.)

Not applicable

5.3 Consent – Other Considerations

5.3.1 Non-English Speaking Subjects

Not planned at this time, although, if subjects who do not speak English will be enrolled, short form and oral translation process will be used to obtain informed consent.

5.3.2 Cognitively Impaired Adults

5.3.2.1 Capability of Providing Consent

Not applicable

5.3.2.2 Adults Unable To Consent

Not applicable

5.3.2.3 Assent of Adults Unable to Consent

Not applicable

5.3.3 Subjects who are not yet adults (infants, children, teenagers)

5.3.3.1 Parental Permission

Not applicable

5.3.3.2 Assent of subjects who are not yet adults

Not applicable

6.0 HIPAA Research Authorization and/or Waiver or Alteration of Authorization

6.1 Authorization and/or Waiver or Alteration of Authorization for the Uses and Disclosures of PHI

Check all that apply:

Not applicable, no identifiable protected health information (PHI) is accessed, used or disclosed in this study. [Mark all parts of sections 6.2 and 6.3 as not applicable]

- Authorization will be obtained and documented as part of the consent process.** *[If this is the only box checked, mark sections 6.2 and 6.3 as not applicable]*
- Partial waiver is requested for recruitment purposes only (Check this box if patients' medical records will be accessed to determine eligibility before consent/authorization has been obtained).** *[Complete all parts of sections 6.2 and 6.3]*
- Full waiver is requested for entire research study (e.g., medical record review studies).** *[Complete all parts of sections 6.2 and 6.3]*
- Alteration is requested to waive requirement for written documentation of authorization (verbal authorization will be obtained).** *[Complete all parts of sections 6.2 and 6.3]*

6.2 Waiver or Alteration of Authorization for the Uses and Disclosures of PHI

6.2.1 Access, use or disclosure of PHI representing no more than a minimal risk to the privacy of the individual

6.2.1.1 Plan to protect PHI from improper use or disclosure

Not applicable

6.2.1.2 Plan to destroy identifiers or a justification for retaining identifiers

Not applicable

6.2.2 Explanation for why the research could not practicably be conducted without access to and use of PHI

The information to be gathered is just for the recruitment purpose. Without it the PI could not identify the eligible subjects. This partial waiver is only for recognize the eligibility of study subjects. Obtaining consent from every subjects come for EMR would be prohibitive, resource exhaustive, and potentially cause confidentiality issues for the ones not be eligible for the study.

6.2.3 Explanation for why the research could not practicably be conducted without the waiver or alteration of authorization

The projects requires look at medical records to identify eligible subjects. Obtaining consent from every subjects come for EMR would be prohibitive, resource exhaustive, and potentially cause confidentiality issues for the ones not be eligible for the study.

6.3 Waiver or alteration of authorization statements of agreement

Not applicable

7.0 Study Design and Procedures

7.1 Study Design

This is a prospective data collection study which patients with non-pedunculated large polyps $\geq 20\text{mm}$ undergoing endoscopic mucosal resection (EMR with adjuvant Hybrid Argon Plasma Coagulation (APC) of the base and edges of the polypectomy site to fulgurate any potential microscopic residual disease. Resected polyps will be sent to the pathology laboratory where pathologist determine the final diagnosis of the polyps as per standard of care. We will collect the detail of the procedure, including,

general procedure details, polyp characteristic, details of any adverse event may happen and the details of 6 months follow up colonoscopy procedure.

7.2 Study Procedures

Consent and basic demographics will be garnered by the PI, Co-investigators or research associate in the pre-procedure area prior to bringing the patient to the endoscopy unit.

Whether or not the patients choose to participate in this study, subject will undergo the scheduled colonoscopy in the same manner as any patient presently referred for resection of large polyps. Patients will have undergone colonoscopy prep as it is standard at each center. All exams will be performed using high-definition colonoscopes with digital chromoendoscopy capability (e.g. Olympus 190 series).

Lesions will be identified using conventional colonoscopic views. Polyp characteristics will be recorded. Endoscopic mucosal resection (EMR) will be used for all resections: the polyp will be submucosally injected, so that the lesion will lift and demarcate from the submucosal layer. The submucosal injection creates a “cushion” between the mucosa and the muscularis propria. The idea is that mucosal lesions can be more safely removed. The applied injectate fluid will contain a lifting agent e.g. NaCl 0.9% and a dye agent e.g. methylene blue. The polyp will be resected with electrocautery snare. Following the resection of the polyp with the snare the submucosal area will be reinjected with saline (NaCl 0.9%) and then thermally ablated using APC (Erbe Hybrid APC). Finally thermal ablation of the resection site with the hybrid APC will occur using start settings. Once resection is considered complete the mucosal defect may be closed with clips for situations include but not limited to control bleeding during the polyp resection. Patients will be monitored continuously as is routine for any colonoscopy performed in our institution. Patients will be observed for in the recovery room before discharge for any sign of complications. (See appendix 1) We will collect the detail of the procedure, including, general procedure details, polyp characteristic, details of any adverse event may happen and the details of 6 months follow up colonoscopy procedure.

7.2.1 EXAMPLE: Visit 1 or Day 1 or Pre-test, etc. (format accordingly)

Patients will be contacted by phone 30 days post procedure to assess for any possible complications. (See appendix 2).

7.2.2 EXAMPLE: Visit 2 or Day 2 or Post-test, etc. (format accordingly)

A follow-up colonoscopy will be scheduled 6 months following the EMR procedure to evaluate for any recurrent polyp.

This is a standard of care for resection of large polyps

7.3 Duration of Participation

For all of the subjects it will take 6 months to complete the study. A follow up colonoscopy will schedule and perform 6 months post-procedure to assess recurrence rate.

8.0 Subject Numbers and Statistical Plan

8.1 Number of Subjects

We're going to enroll 40 patients with detected colon polyps ≥ 20 mm that referred to Hershey Medical Center for EMR colonoscopy.

8.2 Sample size determination

We shall assume a recurrent rate of 5% for the APC assisted EMR. A sample size of 40 subjects provide 60% power of rejecting $H_0: \pi = 15\%$ in a one-sided test, which is reasonable for a pilot study.

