8.3 Statistical methods

The statistical plan for this study was designed with the assistance of [name] with Penn State Public Health Sciences. The primary end point is the rate (proportion of patients) of local recurrent or residual neoplasia at 6 months for the Hybrid Argon Plasma Coagulation (APC) assisted EMR. Estimate of this recurrent rate will provided with 95% exact binomial confidence limits, which will then be compared to the historical rate of 15-20% recurrent rate for EMR alone. Statistical significance will be declared if the upper limit is smaller than 15%. Even when significance is not reached, the confidence interval provides the plausible range of the local recurrent rate of the APC assisted EMR and helps to decide if a future study with a larger sample size is warranted.

Summary statistics such as percentage of male/female patients, percentage of polyps within the different location of colon, mean diameter of polyps, percentage rate of neoplasia recurrence after 6 months, the percentage of each type of Polyps (Ip, Ila, I Ib, I Ic, etc), and Percentage of successful resection will also be provided. SPSS 22 statistical software shall be used to perform statistical analysis.

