16.2 Feasibility of recruiting the required number of subjects

A total of 40 patients are needed for this study. Approximately, 170 colonic EMR performed at Hershey medical center per year. 100-125 of these EMR are done to remove polyps >2cm. We anticipate complete enrollment in 6 months.

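### The stated 60% power does not belong to the trial's success rule: requiring the upper limit of the two-sided 95% exact interval to fall below 15% gives 39.9% power with 40 patients

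*Combined protocol and SAP*

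**What the plan says.** Section 8.2 (Sample size determination) sets the planning rate: "We shall assume a recurrent rate of 5% for the APC assisted EMR". It then states that "A sample size of 40 subjects provide 60% power of rejecting" a null rate of 15% "in a one-sided test, which is reasonable for a pilot study". It names neither a significance level nor a method of calculation.

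Section 8.3 (Statistical methods) defines the analysis: "Estimate of this recurrent rate will provided with 95% exact binomial confidence limits". The benchmark for that estimate is external and is taken from past experience with EMR, not from a control arm. The success criterion follows: "Statistical significance will be declared if the upper limit is smaller than 15" per cent. If that is not met, "the confidence interval provides the plausible range of the local recurrent rate" and is to help decide on a larger study.

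Section 16.2 repeats the number: "A total of 40 patients are needed for this study". No allowance for loss before the 6-month colonoscopy is given.

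**The concern.** The power in 8.2 is quoted for an unspecified one-sided test, while the decision is made by the confidence limit in 8.3. The 8.3 text speaks of limits in the plural and of an interval giving a range, so the plain reading is the two-sided exact (Clopper-Pearson) interval. Its upper limit cuts off 2.5% in one tail, which is stricter than a one-sided 5% test. With a binomial count from 40 patients, each extra recurrence allowed moves power by tens of percentage points, so the difference is large.

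Two things are at stake. The 60% figure was judged acceptable for a pilot, and nobody has made that judgement about the power the rule really has. In addition, a result of 2 in 40 counts as success under one reading of the rule and failure under the other, so the choice has to be fixed before results are seen.

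**Working it through.** **Inputs.** n = 40, null rate p0 = 0.15 and alternative p1 = 0.05 (8.2); 95% exact limits with success if the upper limit is below 15% (8.3). The significance level behind the 60% is not given, so one-sided 0.05 and 0.025 are both tried as assumptions.

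**1. Where the 60% may come from.** The one-sample normal approximation is

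power = Φ[(p0 − p1 − z·√(p0(1−p0)/n)) / √(p1(1−p1)/n)].

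Here √(0.15×0.85/40) = 0.0565 and √(0.05×0.95/40) = 0.0345.

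- One-sided 0.05 (z = 1.645): (0.10 − 1.645×0.0565)/0.0345 = 0.207, so power is 58.2%.
- One-sided 0.025 (z = 1.960): power is 37.9%.

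The arcsine approximation is power = Φ(h√n − z), with h = 2·arcsin√0.15 − 2·arcsin√0.05 = 0.344.

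- One-sided 0.025: 0.344×√40 − 1.960 = 0.218, so power is 58.6%.
- One-sided 0.05: power is 70.3%.

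So 60% is approximately reproduced by two large-sample formulas (58.2% and 58.6%). Neither is the exact test in 8.3.

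**2. What the 8.3 rule allows.** With x recurrences, the upper exact limit is the 0.975 quantile (two-sided 95%) or the 0.95 quantile (one-sided 95%) of a Beta(x+1, n−x) distribution. Power is P(X ≤ x) at 5% and type I error is P(X ≤ x) at 15%, with X binomial on 40 patients.

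| Recurrences | Two-sided 95% upper limit | One-sided 95% upper limit | P(X ≤ x) at 5% | P(X ≤ x) at 15% |
|---|---|---|---|---|
| 0 | 8.8% | 7.2% | 12.9% | 0.2% |
| 1 | 13.2% | 11.3% | 39.9% | 1.2% |
| 2 | 16.9% | 14.9% | 67.7% | 4.9% |
| 3 | 20.4% | 18.3% | 86.2% | 13.0% |

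- *Two-sided 95% interval:* the last passing row is x = 1. Power = 0.95⁴⁰ + 40×0.05×0.95³⁹ = 0.1285 + 0.2706 = 39.9%. Type I error is 1.2%.
- *One-sided 95% bound:* the last passing row is x = 2. Power is 67.7% and type I error 4.9%.

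The attainable exact powers go 12.9%, 39.9%, 67.7%, 86.2%. None is 60%.

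**3. Other ways to express the gap.** Under the two-sided rule, P(X ≤ 1) reaches 60% only when the true rate is about 3.4%. The planning rate itself corresponds to 0.05×40 = 2 recurrences, which fails.

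**4. Incomplete follow-up.** Under the two-sided rule, 35 to 39 evaluable patients still allow 1 recurrence (power 47.2% down to 41.3%), while 30 to 34 allow none (21.5% down to 17.5%). Under the one-sided rule, losing a single patient matters: 2 of 39 has an upper bound of 15.3% and fails, so the cut-off drops to 1 and power to 41.3%.

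**The case against.** The best defence is that 60% is not a miscalculation. It is close to a legitimate approximation for a one-sided 5% test, and 8.2 does say one-sided. If the upper limit in 8.3 was meant as the matching one-sided 95% bound, exact power is 67.7% and the stated figure is conservative. The study is also described as a pilot, its type I error is not inflated, and 8.3 tells the reader to use the interval when significance is missed.

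Part of this stands. The fault is a mismatch between two sections, not a slip within one formula, and the 39.9% depends on the two-sided reading. The instruction to use the interval also limits, without removing, the risk that a miss is over-read as evidence against Hybrid APC: a reader who believes power was 60% will still give a non-significant result too much weight.

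The rest does not rescue the figure. The two-sided reading is the ordinary one for the words used in 8.3, and on the other reading the power is still not 60%. The pilot label was attached to 60%, so it cannot excuse a lower value that was never stated.

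**Conclusion.** The point holds. For the success rule as written in 8.3, read as the two-sided 95% exact interval, 40 evaluable patients give 39.9% power at a true rate of 5%, about 20 percentage points below the stated 60%. If the planning assumption is correct, the trial misses its criterion about 60% of the time (100% − 39.9% = 60.1%).

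The assumptions are independent patients, all 40 assessed at 6 months, and the two-sided reading. Relaxing the last gives 67.7%, so the statement that 60% does not belong to the decision rule is true on either reading.

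**What to change.** Make 8.2 and 8.3 describe the same test, and state the significance level, the maximum number of recurrences and the exact power.

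- **(a) Keep the 8.3 rule.** State that the limit is the upper end of the two-sided 95% exact interval (nominal one-sided 2.5%), that success means at most 1 recurrence in 40, and that power at 5% is about 40% with actual type I error 1.2%. This corrects the figure without changing the design. The cost is a less favourable power statement.
- **(b) Change the rule to match the one-sided wording of 8.2.** Declare significance on the one-sided 95% exact upper bound: at most 2 recurrences in 40, power 68%, actual type I error 4.9%. Continue to report the two-sided 95% interval descriptively. This is a design choice that loosens the nominal one-sided level from 2.5% to 5%. The text should say that 2 recurrences pass only if all 40 are assessed, and that power falls to 41.3% with 39.

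Either option is a wording change needing no extra patients, visits or data, and should be settled before outcome data are examined.
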